8.3.2 Direct access to source data and documents

The investigator /institution will allow site trial-related monitoring, audits, IRB / IEC review and regulatory inspections. Direct access must be provided to the CRF and all source documents/data, including progress notes, copies of laboratory and medical test results, which must be available at all times for review by the Clinical Research Associate, auditor and regulatory inspector (e.g. FDA). They may review all CRFs and informed consents. The accuracy of the data will be verified by direct comparison with the source documents described in Section [8.3.1](#). The sponsor will also monitor compliance with the protocol and GCP.

8.3.3 Storage period of records

Trial site:

The trial site(s) must retain the source and essential documents (including ISF) according to the local requirements valid at the time of the end of the trial.

Sponsor:

The sponsor must retain the essential documents according to the sponsor's SOPs.

8.4 EXPEDITED REPORTING OF ADVERSE EVENTS

BI is responsible to fulfil their legal and regulatory reporting obligation in accordance with regulatory requirements.

8.5 STATEMENT OF CONFIDENTIALITY AND SUBJECT PRIVACY

Individual subject data obtained as a result of this trial is considered confidential and disclosure to third parties is prohibited with the exceptions noted in section [8.7](#).

Data protection and data security measures are implemented for the collection, storage and processing of patient data in accordance with the principles 6 and 12 of the WHO GCP handbook.

Personalised treatment data may be given to the subject's personal physician or to other appropriate medical personnel responsible for the subject's welfare. Data generated at the site as a result of the trial need to be available for inspection on request by the participating physicians, the sponsor's representatives, by the IRB / IEC and the regulatory authorities.

8.5.1 Collection, storage and future use of biological samples and corresponding data

Measures are in place to comply with the applicable rules for the collection, storage and future use of biological samples and clinical data, in particular

- Sample and data usage has to be in accordance with the informed consent
- The BI-internal facilities storing biological samples from clinical trial participants as well as the external storage facility are qualified for the storage of biological samples collected in clinical trials.
- An appropriate sample and data management system, incl. audit trail for clinical data and samples to identify and destroy such samples according to ICF is in place
- A fit for the purpose documentation (biomarker proposal, analysis plan and report) ensures compliant usage
- A fit for purpose approach will be used for assay/equipment validation depending on the intended use of the biomarker data
- Samples and/or data may be transferred to third parties and other countries as specified in the ICF

8.6 TRIAL MILESTONES

The start of the trial is defined as the date of the enrolment of the first subject in the trial.

The end of the trial is defined as the ‘date of the last visit of the last subject in whole trial’ ('Last Subject Completed').

Early termination of the trial is defined as the premature termination of the trial for any reason before the end of the trial as specified in this protocol.

Temporary halt of the trial is defined as any unplanned interruption of the trial by the sponsor with the intention to resume it.

Suspension of the trial is defined as an interruption of the trial based on a Health Authority request.

The EC/competent authority in each participating EU member state will be notified about the trial milestones according to the laws of each member state.

A final report of the clinical trial data will be written only after all subjects have completed the trial in all countries (EU or non-EU), so that all data can be incorporated and considered in the report.

The sponsor will submit to the EU database a summary of the final trial results within one year from the end of a clinical trial as a whole, regardless of the country of the last patient (EU or non-EU).

8.7 ADMINISTRATIVE STRUCTURE OF THE TRIAL

The trial is sponsored by Boehringer Ingelheim (BI).

The trial will be conducted at the [REDACTED]
[REDACTED], under the supervision of the Principal Investigator. Relevant documentation on the participating (Principal) Investigators (e.g. their curricula vitae) will be filed in the ISF.

BI has appointed a Clinical Trial Leader, responsible for coordinating all required trial activities, in order to

- Manage the trial in accordance with applicable regulations and internal SOPs
- Direct the clinical trial team in the preparation, conduct, and reporting of the trial
- Ensure appropriate training and information of local Clinical Trial Managers, Clinical Research Associates, and investigators of participating trial sites

The trial medication will be provided by the [REDACTED]
[REDACTED]

Safety laboratory tests will be performed by the local laboratory of the trial site ([REDACTED]
[REDACTED]).

Analyses of nintedanib concentrations in plasma will be performed at [REDACTED]
[REDACTED]

On-site monitoring will be performed by BI or a contract research organisation appointed by BI.

Proprietary confidential information © 2021 Boehringer Ingelheim International GmbH or one or more of its affiliated companies

Data management and statistical evaluation will be done by BI according to BI SOPs.

Tasks and functions assigned in order to organise, manage, and evaluate the trial are defined according to BI SOPs. A list of responsible persons and relevant local information can be found in the ISF.

10. APPENDICES

Not applicable.

Proprietary confidential information © 2021 Boehringer Ingelheim International GmbH or one or more of its affiliated companies

## **2. LIST OF ABBREVIATIONS**

See Medicine Glossary:

<http://glossary>

Term	Definition / description
AESI	Adverse event of special interest
ALT	Alanine transaminase
ANOVA	Analysis of variance
AST	Aspartate transaminase
AUC 0-tz	Area under the concentration-time curve of the analyte in plasma over the time interval from 0 to the last quantifiable data point
AUC 0-∞	Area under the concentration-time curve of the analyte in plasma over the time interval from 0 extrapolated to infinity
BMI	Body mass index
CI	Confidence interval
C max	Maximum measured concentration of the analyte in plasma
CSD	Company Standard Displays
CV	Arithmetic coefficient of variation
F/U	Follow Up
gCV	Geometric coefficient of variation
gMean	Geometric mean
Max	Maximum
MedDRA	Medical Dictionary for Regulatory Activities
Min	Minimum
N	Number non-missing observations
P10	10 th percentile
P90	90 th percentile
PKS	PK parameter analysis set
Q1	1 st quartile
Q3	3 rd quartile
RAGe	Report Appendix Generator system
REP	Residual Effect Period
RPM	Report Planning Meeting
SD	Standard deviation

Term	Definition / description
SOC	System organ class
TS	Treated set
WHO-DD	World Health Organization Drug Dictionary

### **3. INTRODUCTION**

As per ICH E9 (1) the purpose of this document is to provide a more technical and detailed elaboration of the principal features of the analysis described in the protocol, and to include detailed procedures for executing the statistical analysis of the primary and secondary variables and other data.

This Trial statistical analysis plan (TSAP) assumes familiarity with the Clinical Trial Protocol (CTP), including Protocol Amendments. In particular, the TSAP is based on the planned analysis specification as written in CTP Section 7 “Statistical Methods and Determination of Sample Size”. Therefore, TSAP readers may consult the CTP for more background information on the study, e.g., on trial objectives, study design and population, treatments, definition of measurements and variables, planning of sample size, randomisation.

Study data (including data entered in the RAVE EDC system and external data provided by suppliers) will be stored in a Clinical Data Repository (CDR).

Pharmacokinetic (PK) parameters will be calculated using Phoenix WinNonlinTM software (version 6.3 or higher, [REDACTED]).

The statistical analyses will be performed within the validated working environment CARE, including SASTM (current Version 9.4, by [REDACTED]), and a number of SASTM-based tools (e.g., macros for the analyses of AE data or laboratory data; Report Appendix Generator system (RAGe) for compilation/formatting of the CTR appendices).

#### **4. CHANGES IN THE PLANNED ANALYSIS OF THE STUDY**

All analyses as planned in the CTP will be performed and are described in more detail in this TSAP.

## **5. ENDPOINTS(S)**

### **5.1 PRIMARY ENDPOINT(S)**

#### **Section 2.1.2 of the CTP:**

*The following pharmacokinetic parameters will be determined for nintedanib:*

- *AUC0-tz (area under the concentration-time curve of the analyte in plasma over the time interval from 0 to the last quantifiable data point)*
- *Cmax (maximum measured concentration of the analyte in plasma)*

### **5.2 SECONDARY ENDPOINT(S)**

#### **5.2.1 Key secondary endpoint(s)**

[figure not shown]
This section is not applicable as no key secondary endpoints have been defined in the CTP.

#### **5.2.2 Secondary endpoint(s)**

#### **Section 2.1.3 of the CTP:**

*The following pharmacokinetic parameters will be determined for nintedanib:*

[figure not shown]
- *AUC0-∞ (area under the concentration-time curve of the analyte in plasma over the time interval from 0 extrapolated to infinity)*

#### **Safety and tolerability endpoints**

#### **Section 2.2.2.2 of the CTP: Safety and tolerability of nintedanib will be assessed based on:**

- *Adverse events (including clinically relevant findings from the physical examination)*
- *Safety laboratory tests*
- *12-lead ECG*
- *Vital signs (blood pressure, pulse rate)*

## **6. GENERAL ANALYSIS DEFINITIONS**

### **6.1 TREATMENT(S)**

For basic study information on investigational products and selection of doses, please see CTP Sections 3 and 4.

The study will be performed as a randomised, open-label, two-way cross-over trial. The treatments will be 100 mg nintedanib given as 4 capsules à 25 mg (T) administered to subjects in the fed state and 100 mg nintedanib given as 1 capsule à 100 mg (R) administered to subjects in the fed state. In total, it was planned to assign 20 healthy male subjects to the 2 treatment sequences RT or TR.

There will be a washout period of at least 7 days between the treatments.

For details of dosage and formulation see Table 6.1: 1 below:

Table 6.1: 1 Treatments and labels used in the analysis

Treatment	Short label
R Nintedanib, 1 capsule à 100 mg, qd, fed	NIN 1*100mg
T Nintedanib, 4 capsules à 25 mg, qd, fed	NIN 4*25mg

**Section 1.2.1 of CTP:** *For this trial using two single doses of 100 mg nintedanib in adult healthy volunteers, a Residual Effect Period (REP) of 7 days is used. This is a conservative estimate of the period after the last single dose with measurable drug levels and/or pharmacodynamic effects is still likely to be present.*

The following study phases will be defined for the analysis of adverse events (AEs):

- **Screening**
  - Ranging from 0:00h on day of informed consent until administration time of nintedanib in treatment period 1.
- **On treatment** (labelled “NIN 1\*100mg”, “NIN 4\*25mg”)
  - Ranging from the administration time of nintedanib until 7 days (168 h) thereafter OR until next administration of nintedanib, whatever occurs first.
- **Follow-up** (labelled “F/U NIN 1\*100mg”, “F/U NIN 4\*25mg”)
  - Ranging from the end of REP until the next administration of nintedanib OR until trial termination, whatever occurs first.

**Section 7.3.4 of the CTP:** *Note that AEs occurring after the last per protocol contact but entered before final database lock will be reported to Pharmacovigilance only and will not be captured in the trial database.*

The following AE displays will be provided in the report:

**A)** Section 15.3 and Appendix 16.1.13.1.8 (for ClinicalTrials.gov and EudraCT only) of the CTR displays:

In these displays, the on treatment phase will be analysed (labelled with the name of the study treatment (short label)). Screening and follow-up periods will not be included in this analysis.

The following total will be provided in addition (Section 15.3 only):

- a total over all on treatment phases included in this analysis ("Total")

**B)** Section 15.4 of the CTR displays:

- Screening
- On treatment (labelled with the name of the study treatment (short label))
- Follow-up phases (labelled "F/U NIN 1\*100mg", "F/U NIN 4\*25mg")

For detailed information on the handling of the treatments refer to Technical TSAP ADS plan and Analysis Data Reviewers guide.

## 6.2        IMPORTANT PROTOCOL DEVIATIONS

Data discrepancies and deviations from the CTP will be identified for all treated subjects.

Consistency check listings (for identification of deviations of time windows) and a list of protocol deviations (e.g. deviations in drug administration, in blood sampling times, etc.) will be provided to be discussed at the Report Planning Meeting (RPM). At this meeting, all manual deviations identified at the sites by the CRAs and deviations too complex to program will be reviewed by the trial team to decide which are considered important. For definition of important protocol deviations (iPD), and for the process of identification of these, refer to the Boehringer Ingelheim (BI) SOP "Identify and Manage Important Protocol Deviations (iPD)" (2).

**Section 7.3 of the CTP:** *Important protocol deviation (iPD) categories will be suggested in the iPD specification file, iPDs will be identified no later than in the Report Planning Meeting, and the iPD categories will be updated as needed.*

If any iPDs are identified, they are to be summarised into categories and will be captured in the iPD specification file and the decision log. The iPD specification file (e.g. the DV domain specifications) will be stored within the TMF in EDMS.

The iPDs will be summarized and listed in the CTR.

### 6.3 SUBJECT SETS ANALYSED

#### Section 7.3 of the CTP:

- *Treated set (TS): The treated set includes all subjects who were randomized and treated with at least one dose of study drug. The treated set will be used for safety analyses.*
- *Pharmacokinetic parameter analysis set (PKS): This set includes all subjects in the treated set (TS) who provide at least one PK endpoint that was defined as primary or secondary and was not excluded due to a protocol deviation relevant to the evaluation of PK or due to PK non-evaluability (as specified in the following subsection 'Pharmacokinetics'). Thus, a subject will be included in the PKS, even if he/she contributes only one PK parameter value for one period to the statistical assessment. Descriptive and model based analyses of PK parameters will be based on the PKS.*

[...]

*Plasma concentration data and parameters of a subject will be included in the statistical pharmacokinetic (PK) analyses if they are not flagged for exclusion due to a protocol deviation relevant to the evaluation of PK (to be decided no later than in the Report Planning Meeting) or due to PK non-evaluability (as revealed during data analysis, based on the criteria specified below). Exclusion of a subject's data will be documented in the CTR.*

*Relevant protocol deviations may be*

- *Incorrect trial medication taken, i.e. the subject received at least one dose of trial medication the subject was not assigned to*
- *Incorrect dose of trial medication taken*
- *Use of restricted medications*

*Plasma concentrations and/or parameters of a subject will be considered as non-evaluable, if for example*

[figure not shown]
- *The subject experienced emesis that occurred at or before two times median  $t_{max}$  of the respective treatment (Median  $t_{max}$  is to be determined excluding the subjects experiencing emesis)*
- *A predose concentration is  $>5\% C_{max}$  value of that subject*
- *Missing samples/concentration data at important phases of PK disposition curve*

*Plasma concentration data and parameters of a subject which is flagged for exclusion will be reported with its individual values but will not be included in the statistical analyses. Descriptive and inferential statistics of PK parameters will be based on the PKS.*

The descriptive analysis of PK concentrations will be based on the ADS ADPC as described at the beginning of [Section 7](#).

Table 6.3: 1 Subject sets analysed

Class of endpoint	Subject set	
	TS	PKS
Analyses of PK endpoints		X
Safety parameters	X	
Demographic/baseline parameters	X	
Important protocol deviations	X	
Disposition	X	
Exposure	X	

## 6.5 POOLING OF CENTRES

This section is not applicable, because the study was performed in only one centre.

## 6.6 HANDLING OF MISSING DATA AND OUTLIERS

Handling of missing data and outliers will be performed as described in the CTP, Section 7.5.

The only exceptions where imputation might be necessary for safety evaluation are AE dates. Missing or incomplete AE dates are imputed according to BI standards (see BI-KMED-BDS-HTG-0035) (4).

Missing data and outliers of PK data are handled according to BI standards (see BI-KMED-TMCP-MAN-0012 (5) and BI-KMED-TMCP-MAN-0014 (6)).

## 6.7 BASELINE, TIME WINDOWS AND CALCULATED VISITS

The baseline value is defined as the last measurement before administration of nintedanib in each treatment period.

**Section 6.1 of the CTP:** *The acceptable time windows for screening, study measurements and assessments scheduled to occur 'before' trial medication administration on Day 1, and the end of trial examination are provided in the CTP Flow Chart.*

*If not stated otherwise in the Study Protocol Flow Chart, the acceptable deviation from the scheduled time for laboratory tests will be  $\pm 2$  h.*

*For planned blood sampling times, refer to the CTP Flow Chart. Starting from planned time of 48 hours after drug administration (and beyond) a time window of +/- 120 minutes will be allowed for all procedures.*

Adherence to time windows will be checked via the consistency check listings at the RPM.

Unscheduled measurements of laboratory data and vital signs data will be assumed to be repeat measurements of the most recent scheduled measurement (e.g. for follow-up or confirmation of a particular value). Therefore, unscheduled measurements will be assigned to the planned time point of the previous scheduled measurement.

## **7. PLANNED ANALYSIS**

Safety analysis (refer to [Section 7.8](#)) will be performed by [REDACTED] and will be presented in Sections 15.1 to 15.4 of the CTR and in Appendix 16.2 and 16.1.13.1.

Inferential statistical analyses of PK endpoints (refer to [Section 7.4](#) and [Section 7.5.2](#)) will also be performed by [REDACTED] and will be presented in Section 15.5 of the CTR and in Appendix 16.1.13.3.

Descriptive data analysis of PK endpoints and concentrations will be performed by the department of [REDACTED] at [REDACTED] and will be presented in Section 15.6 of the CTR.

The format of the listings and tables will follow the BI standards with the exception of those generated for PK-calculations following BI standards for PK/PD analysis ([7](#)).

The individual values of all subjects will be listed, sorted by treatment sequence, subject number and visit. The listings will be included in Appendix 16.2 of the CTR.

For end-of-text tables, the set of summary statistics for non-PK parameters is:

N	number non-missing observations
Mean	arithmetic mean
SD	standard deviation
Min	minimum
Median	median
Max	maximum

For analyte concentrations, the following descriptive statistics will additionally be calculated:

CV	arithmetic coefficient of variation
gMean	geometric mean
gCV	geometric coefficient of variation

For PK parameters, the following descriptive statistics will additionally be calculated:

CV	arithmetic coefficient of variation
gMean	geometric mean
gCV	geometric coefficient of variation
P10	10th percentile
Q1	1st quartile
Q3	3rd quartile
P90	90th percentile

The data format for descriptive statistics of concentrations will be identical to the data format of the respective concentrations. The descriptive statistics of PK parameters will be calculated using the individual values with the number of decimal places as provided by the evaluation program. Then the individual values as well as the descriptive statistics will be reported with three significant digits in the CTR.

Tabulations of frequencies for categorical data will include all possible categories and will display the number of observations in a category as well as the percentage (%) relative to the respective treatment group (unless otherwise specified, all subjects in the respective subject set whether they have non-missing values or not).

The precision for percentages should be one decimal point, unless the denominator is smaller than 100 (in all treatment columns), in which case percentages are given in integer numbers. The category missing will be displayed only if there are actually missing values.

#### Exclusion of PK parameters

The ADS “ADPP” (PK parameters) contains column variables APEXC and APEXCO indicating inclusion/exclusion (APEXC) of a PK parameter and an analysis flag comment (APEXCO). All analyses based on the PKS will include parameters if they are not flagged for exclusion, that is APEXC is equal to “Included”.

#### Exclusion of PK concentrations

The ADS “ADPC” (PK concentrations per time-point or per time-interval) contains column variables ACEXC and ACEXCO indicating inclusion/exclusion (ACEXC) of a concentration and an analysis flag comment (ACEXCO). Exclusion of a concentration depends on the analysis flag comment ACEXCO. For example, if ACEXCO is set to ‘ALL CALC’, the value will be excluded for all types of analyses based on concentrations. If ACEXCO is set to ‘DESC STATS’ the value will be excluded from descriptive evaluations per planned time point/time interval. If ACEXCO contains the addition ‘TIME VIOLATION’ or ‘TIME DEVIATION’ the value can be used for further analyses based on actual times. If ACEXCO is set to ‘HALF LIFE’, the value will be excluded from half-life calculation (and, as a consequence, any calculation that relies on  $\lambda_z$ ) only; the value is included for all other analyses.

## **7.1 DEMOGRAPHIC AND OTHER BASELINE CHARACTERISTICS**

Only descriptive statistics are planned for this section of the report, based on the TS. The data will be summarised by treatment sequence and in total.

## **7.2 CONCOMITANT DISEASES AND MEDICATION**

Only descriptive statistics are planned for this section of the report, based on the TS.

Concomitant diseases will be coded using the coding system of the Medical Dictionary for Drug Regulatory Activities (MedDRA). Medications will be coded using the World Health Organization Drug Dictionary (WHO-DD). The coding version number will be displayed as a footnote in the respective output.

The diagnoses and medications will be listed. Subjects without any concomitant diagnoses or concomitant therapies should be marked with a “No” in the respective column.

The relevance of the concomitant therapies to the evaluation of PK will be decided no later than at the RPM.

### **7.3 TREATMENT COMPLIANCE**

Only descriptive statistics are planned for this section of the report.

It is not intended to list the compliance separately. Any deviation from complete intake will be addressed in the RPM (see [Section 6.2](#)) and described in the CTR.

### **7.4 PRIMARY ENDPOINT(S)**

For nintedanib, the relative bioavailability will be investigated on the basis of the primary PK endpoints  $AUC_{0-tz}$  and  $C_{max}$  (see [Section 5.1](#)).

#### **7.4.1 Primary analysis of the primary endpoints**

##### **Section 7.3.1 of the CTP:**

*The statistical model used for the analysis of the primary endpoints will be an analysis of variance (ANOVA) model on the logarithmic scale. That is, the PK endpoints will be log-transformed (natural logarithm) prior to fitting the ANOVA model. This model will include effects accounting for the following sources of variation: sequence, subjects within sequences, period and treatment. The effect 'subjects within sequences' will be considered as random, whereas the other effects will be considered as fixed. The model is described by the following equation:*

$y_{ijkm} = \mu + \zeta_i + s_{im} + \pi_j + \tau_k + e_{ijkm}$ , where  
 $y_{ijkm}$  = logarithm of response measured on subject  $m$  in sequence  $i$  receiving treatment  $k$  in period  $j$ ,  
 $\mu$  = the overall mean,  
 $\zeta_i$  = the  $i^{th}$  sequence effect,  $i = 1, 2$ ,  
 $s_{im}$  = the effect associated with the  $m^{th}$  subject in the  $i^{th}$  sequence,  $m = 1, 2, \dots, 20$   
 $\pi_j$  = the  $j^{th}$  period effect,  $j = 1, 2$ ,  
 $\tau_k$  = the  $k^{th}$  treatment effect,  $k = 1, 2$ ,  
 $e_{ijkm}$  = the random error associated with the  $m^{th}$  subject in sequence  $i$  who received treatment  $k$  in period  $j$ .

where  $s_{im} \sim N(0, \sigma_B^2)$  i.i.d.,  $e_{ijkm} \sim N(0, \sigma_W^2)$  i.i.d. and  $s_{im}$ ,  $e_{ijkm}$  are independent random variables.

*Point estimates for the ratios of the geometric means (test/reference) for the primary endpoints (see CTP Section 2.1) and their two-sided 90% confidence intervals (CIs) will be provided.*

*For each endpoint, the difference between the expected means for log(T)-log(R) will be estimated by the difference in the corresponding adjusted means (Least Squares Means). Additionally their two-sided 90% confidence intervals will be calculated based on the residual error from the ANOVA and quantiles from the t-distribution. These quantities will then be back-transformed to the original scale to provide the point estimate and 90% CIs for each endpoint.*

The implementation for this analysis will be accomplished by using the CSD macros based on PKS. The following SAS code can be used:

```
PROC MIXED DATA=indata METHOD=REML;
  CLASS subject treatment sequence period;
  MODEL logpk = treatment sequence period / DDFM=KR;
  RANDOM subject(sequence);
  LSMEANS treatment / PDIFF CL ALPHA=0.1;
RUN;
```

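### Would the plain PDIFF in the SAP's example SAS code turn the Test/Reference ratio upside down?

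*SAP*

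**What the plan says.** SAP Section 7.4.1, repeating protocol Section 7.3.1, promises "Point estimates for the ratios of the geometric means (test/reference) for the primary endpoints" with two-sided 90% confidence intervals. On the log scale, "the difference between the expected means for log(T)-log(R) will be estimated by the difference in the corresponding adjusted means", and the estimate and its limits are then back-transformed. Protocol Section 7.2 and the synopsis also give the ratio as test over reference.

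The SAP then says that the analysis will be carried out with the CSD macros on the PKS, and offers a short PROC MIXED step as code that may be used. Its class statement is "CLASS subject treatment sequence period" and its contrast request is "LSMEANS treatment / PDIFF CL ALPHA=0.1". The printed step has no ORDER= option, control level or ESTIMATE statement. It also contains no log transformation and no exponentiation.

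SAP Table 6.1: 1 lists Reference as "R Nintedanib, 1 capsule à 100 mg, qd, fed" and gives Test under code T as "Nintedanib, 4 capsules à 25 mg, qd, fed". The short labels are `NIN 1*100mg` and `NIN 4*25mg`.

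**The concern.** A bare PDIFF reports the earlier-sorted level minus the later one. Under the SAP's own labels Reference sorts first, so the printed row runs opposite to the defined effect, and no line of the code reverses it. Someone who exponentiated that row without checking would report Reference/Test for AUC0-tz, Cmax and AUC0-∞.

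This ratio is the trial's only inferential result, and it is meant to characterise a new 25 mg capsule in support of a paediatric submission. Inverted, lower exposure from the new capsule would read as higher exposure. Protocol Section 7.2 sets no acceptance range, so no pass/fail rule would draw attention to the direction.

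**Working it through.** **Which way the printed row runs.** Assume standard PROC MIXED behaviour (class levels in ascending order, PDIFF as earlier minus later). SAS itself was not run.

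| Coding of `treatment` | Sorts first | Sorts second | Default difference |
|---|---|---|---|
| Letter code | R | T | R − T |
| Short label | `NIN 1*100mg` | `NIN 4*25mg` | R − T |
| Long label | the 1-capsule text | the 4-capsule text | R − T |

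Every label form in Table 6.1: 1 puts Reference first. A dataset coding that sorted Test first would print T − R. The coding of `indata` is not given. SAP Section 6.1 refers to the technical ADS plan and the reviewers guide for treatment handling.

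**The plan's own precision figure.** Protocol Section 7.7 assumes a 30% intra-individual CV and 18 evaluable subjects, for a precision (upper limit divided by estimate) of 1.25 with 95% probability.

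- σ_w = √ln(1 + 0.30²) = 0.2936
- Expected log half-width at n = 18: t(0.95, 16) × σ_w × √(2/18) = 1.746 × 0.2936 × 0.3333 = 0.1708, so expected precision is exp(0.1708) = 1.186
- With 95% assurance: 0.1708 × √(χ²(0.95, 16)/16) = 0.1708 × 1.282 = 0.219, and exp(0.219) = 1.245, which is below 1.25
- At n = 17 the assured precision is 1.256, which misses the target

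The stated 18 is reproduced.

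**What an uncorrected row would show.** If the printed difference is d with limits (L, U) for R − T, the wanted result is exp(−d) with limits exp(−U) and exp(−L). With the expected half-width of 0.1708:

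| T/R (90% CI) | Same data read as R/T (90% CI) |
|---|---|
| 0.85 (0.717 to 1.008) | 1.176 (0.992 to 1.396) |
| 0.90 (0.759 to 1.068) | 1.111 (0.937 to 1.318) |
| 1.00 (0.843 to 1.186) | 1.000 (0.843 to 1.186) |
| 1.10 (0.927 to 1.305) | 0.909 (0.766 to 1.078) |

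The log half-width is 0.1708 in both columns. Only the sign differs, and taking reciprocals restores the result exactly.

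**Whether the plan leads there.**

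1. What the text sends to back-transformation is the estimate of log(T) − log(R) and its interval. An analyst following it either requests that direction or flips the sign. It does not tell anyone to exponentiate whatever row PDIFF prints.
2. The code is not a complete route from data to reported ratio. The exponentiation is missing, and so is any step that picks out and orients the contrast. All of this is left to the macros or the analyst.
3. The same LSMEANS statement prints the adjusted mean of each treatment. The defined effect is LSMEAN(T) − LSMEAN(R), so a reversed sign shows against the two means in the same output.
4. SAP Section 7 also requires geometric means of the PK parameters, reported in CTR Section 15.6, with the ratios in Section 15.5. A T/R of 1.18 beside a clearly lower geometric mean for Test would be inconsistent on its face.

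**The case for a change.** The strongest case for acting is that a SAP exists to give technical detail, so its code should produce the quantity its text defines, and one option in one line would ensure that. The protocol's example interval, 0.80 to 1.25, is its own reciprocal (1/0.80 = 1.25), so a dry run centred on a ratio of 1.00 would not reveal a reversal. The descriptive geometric means appear in a different report section from the ratios, and no reconciliation step is written down.

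It stands that the example code leaves the direction open and that, with the SAP's labels and default ordering, the raw row would be R minus T. The step from there to a wrong report does not stand. It requires the analyst to set aside the definition directly above the code, the unseen macros to lack a fixed direction, and nobody to compare the ratio with the two means. The documents support none of these. Writing an ESTIMATE statement with coefficients −1 and 1 would not clearly help either, because those coefficients also depend on level order and would invert if Test sorted first.

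**Conclusion.** No change to the plan is needed. The direction of the ratio is stated consistently in the protocol and the SAP. The code is an incomplete, optional illustration whose gap an analyst working from that text would fill correctly. Naming the reference level would make the example clearer but would change no reported estimate, interval, degrees of freedom or sample size.

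The possible error is large if one imagines the raw row being reported (0.85 read as 1.18), but the documents do not show that it would be. This conclusion rests on three things: standard PROC MIXED defaults, not run here; treatment coding and macros that cannot be seen and could print either direction; and the SAP text governing over its example code.
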